9.5 Analysis Populations

The final definition of the analysis sets (ITT, PP and Safety) will be taken at the clean file meeting before database lock.

- The Intention-to-Treat population (ITT) will include all subjects who have undergone surgical intervention.
- The Per Protocol population (PP) will include subjects that have completed the study according to the protocol. Subjects that were incorrectly included or were considered major protocol violators that affect the primary analysis should be removed from the PP population.
- The Safety population consists of all surgically treated subjects

All efficacy analyses will be performed on both ITT and PP populations.

9.6 Primary Outcome Analyses

Primary efficacy analysis will be determined by analysis of change in free-field threshold audiometry: PTA4 (mean of 500, 1000, 2000 and 4000Hz) and change in Adaptive speech recognition in noise (50% performance), from unaided versus Investigational device at 3 months post-surgery visit for the ITT population, using Fisher's two-sided non-parametric permutation test for paired observations at a significance level of 0.05 to demonstrate an improvement in PTA4. Both PTA4 and SNR must be significant at alpha 0.05 for the primary analysis to be considered as confirmative.

See paragraph 9.1 General considerations for further details.

9.7 Secondary Outcome Analyses

See paragraph 9.1 General considerations for details.

9.8 Tertiary Outcome Analyses

See paragraph 9.1 General considerations for details.

9.9 Exploratory Endpoint Analyses

Speech in noise data will be assessed for the total population and separately for the individual sites. Data will be tabulated for comparison, no statistical analysis will be performed.

9.10 Safety Analyses

Primary safety analysis will be performed at 3 months post-surgery.

9.10.1 Implant site evaluation (numbness)

Implant site evaluation (numbness) will be summarised by frequency and percent of 1. No numbness, 2. Numbness over the implant Magnet Assembly area and 3. Numbness over the implant Magnet Assembly area and 2 cm outside the implant Magnet Assembly area by visit.

9.10.2 Adverse events

Separate tabulations of AEs, ADEs, SAEs, SADEs and AESIs will be produced. AEs, ADEs and AESIs will also be produced by severity (mild, moderate or severe) and relationship (related defined as Possibly, Probably and Definitely related). Adverse events will be coded and summarized by number of events and also by number of subject and percent with events.(see section 11.2)

9.10.3 Device deficiency

DDs will be reported by visit as described in 11.3 General considerations.

9.10.4 Concomitant medication

Concomitant medications will be defined as start or end date from surgery to end of study and will be presented by listings.

9.11 Interim Analyses

Not applicable.

10 INFORMED CONSENT PROCESS

The Investigator shall obtain written informed consent from the subject using an approved ICF prior to any clinical investigation related examination or activity. The rationale of the clinical investigation, as well as the risks and benefits, what participation will involve, and alternatives to participation will be explained to the subject. Ample time will be provided for the subject to enquire about details of the clinical investigation and to decide whether to participate.

All questions about the clinical investigation shall be answered to the satisfaction of the subject or the subject's legally acceptable representative. Subjects shall not be coerced or unduly influenced to participate or to continue to participate in a clinical investigation.

Each subject (or their legally authorised representative) and the person who conducted the informed consent discussion, shall sign and date the Informed Consent Form (ICF). Where required, a witness shall sign and personally date the ICF. A copy of the signed ICF shall be given to the subject. The original signed ICF shall be archived in the Investigator's Site File or subject file at the investigational site.

The subject, or the subject's legally authorised representative, shall be informed in a timely manner if new information becomes available that may be relevant to the subject's willingness to continue participation in the clinical investigation. The communication of this information must be documented as an update to the ICF and re-consent of the subject.

11 ADVERSE EVENTS AND DEVICE DEFICIENCIES

11.1 Definitions

11.1.1 Adverse Event

An adverse event (AE) is any untoward medical occurrence, unintended disease or injury, or untoward clinical signs (including abnormal laboratory findings) in subjects, users or other persons whether or not related to the medical device or the procedures required for implant or use.

NOTE 1: This definition includes events related to the medical device or the comparator device.

NOTE 2: This definition includes events related to the procedures involved.

NOTE 3: For users and other persons, this definition is restricted to events related to medical devices.

11.1.2 Adverse Device Effect

An adverse device effect (ADE) is an AE related to the use of a medical device.

NOTE 1: This includes any AE resulting from insufficiencies or inadequacies in the instructions for use, the deployment, the implantation, the installation, the operation, or any malfunction of the medical device.

NOTE 2: This definition includes any event resulting from use error or from intentional misuse of the medical device.

11.1.3 Serious Adverse Event

A serious adverse event (SAE) is any AE that:

- led to a death,
- led to a serious deterioration in the health of the subject that either resulted in:
 - a life-threatening illness or injury, or
 - a permanent impairment of, or damage to, a body structure or a body function, or
 - in-patient hospitalisation or prolonged hospitalisation, or
 - medical or surgical intervention to prevent life-threatening illness or injury or permanent impairment or damage to a body structure or a body function, or
 - Chronic disease.
- led to foetal distress, foetal death or a congenital physical or mental abnormality, or birth defect

NOTE: Planned hospitalisation for a pre-existing condition, or a procedure required by the CIP, without serious deterioration in health, is not considered a SAE.

11.1.4 Serious Adverse Device Effect

A serious adverse device effect (SADE) is an ADE that has resulted in any of the consequences characteristic of a SAE.

11.1.5 Unanticipated Serious Adverse Device Effect

An unanticipated serious adverse device effect (USADE) is a SADE, which by its nature, incidence, severity, or outcome has not been identified in the current version of the Investigator's Brochure (7).

NOTE: An anticipated serious adverse device effect is an effect, which by its nature, incidence, severity, or outcome has been identified in the Investigator's Brochure (7).

11.1.6 Adverse Events of Special Interest

The following AEs are defined as adverse events of special interest (AESIs) and should be reported within 24 hours, after being aware of an event:

- AE that interferes with the daily use of the medical device(s)
- AE at the site of the implant that leads to
 - Revision surgery including explantation
 - Severe soft tissue complication
 - Prescription of antibiotics

11.1.7 Device Deficiency

A DD is an inadequacy of a medical device with respect to its identity, quality, durability, reliability, safety, or performance.

NOTE: Device Deficiencies include malfunctions, use errors, and inadequate labelling or information supplied by the manufacturer.

11.2 Recording and Handling of Adverse Events

Subjects shall be carefully monitored during the clinical investigation and the investigator should enquire about AEs at each visit.

All AEs will be recorded from Screening/Baseline. AE recording will continue for each subject until completion of the final visit. Ongoing SAEs, SADEs and/or AESI will be followed for 30 days, or until resolution or stabilisation of the event, whichever comes first.

Source notes should indicate the evaluation for AEs, even if none to report. All required AEs will be reported if observed, even if anticipated and/or acknowledged as a risk factor in the consent.

All AEs will have the following information documented: start and stop dates, action taken, outcome, severity and investigators opinion on the potential relationship to the Investigational device and investigational procedures. If an AE changes in severity, the most severe (highest) grade will be captured for that event on the Adverse Events CRF.

Adverse events will be summarized by CTCAE to System Organ Class (SOC) and CTCAE term.

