
To compare hearing performance between the Investigational device and a Baha 5 Power Sound Processor on a Baha Softband (preoperative).
	
At fitting, 3 and 6 months compared to preoperative.
 
 • Thresholds audiometry, free-field [PTA4, Mean of 0.5, 1, 2 and 4 kHz]. • Thresholds audiometry, free-field [0.25, 0.5, 0.75, 1.0, 1.5, 2.0, 3.0, 4.0, 6.0 and 8.0 kHz]. • Adaptive speech in noise [signal-to-noise ratio, 50% speech understanding]. • Speech in quiet [% correctly perceived words at 50dB, 65dB and 80dB SPL]. • BC Direct [0.25, 0.5, 0.75, 1.0, 1.5, 2.0, 3.0, 4.0 and 6.0 kHz].
Safety Objective	Safety Outcome measures

Primary safety analysis 3 months post-surgery
	

Implant site evaluation
	
Numbness will be collected from Suture removal and onwards.

Adverse events
	
Information will be collected from Surgery and onwards.

Device deficiency
	
Information will be collected from Surgery and onwards.

Concomitant medication
	
Information will be collected from Surgery and onwards.

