7.4 Safety Evaluations and Procedures

Subjects will be carefully monitored during the study for possible adverse events and appropriate treatment of the subject will be initiated. Any adverse events observed will be fully investigated by the investigator and documented in the CRF including assessment of seriousness, severity (mild, moderate or severe) and relationship to the medical device. The risks and anticipated ADEs for Osia 2 System, as identified in Section 8.3 of the CIP, will be assessed in the clinical study via reporting of all AEs/ADEs from the time of first subject first visit until last subject last visit. The Sponsor will be notified by automatic eCRF alerts when

events are judged as device related or serious. A safety monitor, appointed by the Sponsor, will be contacted regarding events that are uncertain, serious or unexpected.

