#### **3.3.1 Safety**

The Safety population/dataset consists of all surgically treated subjects.

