#### **3.4.4.14 Adverse events**

Separate tabulations of AEs, ADEs, SAEs, SADEs and AESIs will be produced. AEs, ADEs and AESIs will also be produced by severity (mild, moderate or severe) and relationship (related defined as Possibly, Probably and Definitely related). Number of events, number of subject and percent with events by System Organ Class (SOC, CTCAE) and CTCAE term will be presented.

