#### **3.4.4.16 Concomitant medication**

Concomitant medications will be defined as start or end date from surgery to end of study and will be presented by listings.

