Table 14.2.11.1	Adaptive speech recognition in noise and Speech in quiet Osia System vs Softband (ITT Population)
Table 14.2.11.2	Adaptive speech recognition in noise and Speech in quiet Osia System vs Softband (PP Population)
Table 14.2.11.3	Adaptive speech recognition in noise and Speech in quiet Osia System vs Softband (landscape layout) (All patients - ITT Population)
Table 14.2.11.4	Adaptive speech recognition in noise and Speech in quiet Osia System vs Softband (landscape layout) (Mixed/Conductive patients - ITT Population)
Table 14.2.11.5	Adaptive speech recognition in noise and Speech in quiet Osia System vs Softband (landscape layout) (SSD patients - ITT Population)
Table 14.3.1.1	Summary of Adverse Events (Safety Population)
Table 14.3.1.2	Adverse Events (AE), by CTCAE SOC and CTCAE Term (Safety Population)
Table 14.3.1.3	Adverse Device Events (ADE possibly, probably and definitely related), by CTCAE SOC and CTCAE Term (Safety Population)
Table 14.3.1.4	Serious Adverse Events (SAE), by CTCAE SOC and CTCAE Term (Safety Population)
Table 14.3.1.6	Adverse Events of Special Interest (AESI), by CTCAE SOC and CTCAE Term (Safety Population)
Table 14.3.2	Numbness (Safety Population)
Table 14.3.3.1	Device deficiency per visit (Safety Population)
Table 14.3.3.2	Device deficiency (number of events and subjects) (Safety Population)

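### Adverse events are recorded from screening, the safety outcome starts at surgery, and the AE tables have no onset rule to separate the two

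*Protocol*

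**What the plan says.** **When collection starts.** Protocol 11.2: "All AEs will be recorded from Screening/Baseline". Protocol 7.4 has the anticipated risks assessed "via reporting of all AEs/ADEs from the time of first subject first visit until last subject last visit". The schedules of events (protocol Section 3, SAP 1.1) both mark adverse events at the Screening and Baseline visit. The safety objective, in the synopsis (Section 2) and in 6.2, says of adverse events: "Information will be collected from Surgery and onwards".

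**What is tabulated.** SAP 3.4.4.14: "Separate tabulations of AEs, ADEs, SAEs, SADEs and AESIs will be produced", and then "Number of events, number of subject and percent with events by System Organ Class (SOC, CTCAE) and CTCAE term will be presented". Protocol 9.10.2 has the same tabulations and refers back to 11.2 for the events. The table titles in SAP 3.7.2 name the Safety population and nothing more. SAP 3.3.1: "The Safety population/dataset consists of all surgically treated subjects". SAP 3.5.1 limits the first report to data up to 3 months, which is an upper bound only.

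**A contrast.** Concomitant medication has the same mismatch: surgery in the objectives, screening in the schedule. There the SAP settles it in 3.4.4.16: "Concomitant medications will be defined as start or end date from surgery to end of study". Adverse events have no equivalent sentence.

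**The concern.** The Safety population is a rule about people. It removes subjects who were never operated on, but it keeps every recorded event of those who were, whatever its date. A programmer following the SAP would therefore count events that preceded the implant and the operation, although the plan's own safety outcome begins at surgery.

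What is at stake is how the all-AE and SAE tables read. With 30 implanted subjects, each event is visible. SAP 3.4.4.14 breaks AEs, ADEs and AESIs down by relationship but does not list SAEs there, so a pre-operative SAE in Table 14.3.1.4 need not be marked as unrelated.

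**Working it through.** **1. The plan's own figure.** Protocol 9.4 and SAP 3.1 give 7.5 patient-years for the primary safety evaluation. Patient-years = N × follow-up = 30 × 3/12 = 7.5. The figure reproduces, and it is counted from surgery.

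**2. The window over which events are counted.** Under 11.2 it starts at screening. The documents do not give the screening-to-surgery interval, so the lengths below are assumptions. Added time = 30 × weeks/52.

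| Assumed mean interval | Added patient-years | Relative to 7.5 |
|---|---|---|
| 2 weeks | 30 × 2/52 = 1.15 | +15% |
| 4 weeks | 30 × 4/52 = 2.31 | +31% |
| 8 weeks | 30 × 8/52 = 4.62 | +62% |
| 12 weeks | 30 × 12/52 = 6.92 | +92% |

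The last row is hard to reach. Protocol 7.2.5 expects about 4 to 6 months from first consent to last enrolment, and enrolment there means implanted. Twelve weeks is 12/52 × 12 = 2.8 months, or 46% to 69% of that whole period. These figures describe the length of the window. They are not event counts.

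**3. Effect of one event.** One pre-surgery event in a subject with no other event of that class adds one event and 1/30 = 3.3 percentage points of subjects.

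**4. Which tables are exposed.**
- *All AEs (14.3.1.2), SAEs (14.3.1.4) and the summary (14.3.1.1):* exposed. No relationship is required and no onset date is set.
- *ADEs (14.3.1.3):* largely protected. The title requires a possible, probable or definite relationship, and 11.2.2 lists the absence of a temporal relationship with device use or procedures as a criterion for not related. The protection is incomplete. Section 11.1.2 defines an ADE by relation to a medical device, without naming the investigational one. The Baha 5 Power on Softband is used before surgery (5.2). Events whose relatedness cannot be assessed are classed as possibly related (11.2.2).
- *AESIs (14.3.1.6):* little exposed. By 11.1.6 they concern the implant site or daily use of the device.

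**5. Whether a date filter is enough.** Section 11.2 records start and stop dates, so onset on or after surgery can be programmed. It also keeps only the highest severity grade per event. An event that began before surgery and worsened after it would carry a pre-surgery start date, and a plain onset filter would drop it. The rule has to cover this case.

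**The case against.** The strongest reply is that every working instruction to sites (both schedules, 7.4 and 11.2) says screening. Only the objectives table, in its two copies, says surgery. That row sits among the outcome measures beside the primary safety analysis, so it can be read as the outcome window and not as a recording rule. This stands. A reader might infer that sites will start collection at different times, but the documents do not show it. The same reading strengthens the remaining point: if surgery onwards is the outcome window, the tables need to apply it and do not.

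Second, all-causality tables are meant to hold unrelated events, so including an event there does not attribute it to the implant. That also stands. The difficulty is the period counted, not attribution.

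Third, the 7.5 patient-years only supports the sample size. The SAP reports counts and percentages, not rates per patient-year, so no planned statistic divides by the wrong exposure. This is correct.

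Fourth, start dates are on file and the split could be made at reporting. It could, but the choice would then be made with the events in view. It costs almost nothing to make it beforehand, as was done for concomitant medication.

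**Conclusion.** The point holds as a minor one. The stated rules, followed literally, give AE and SAE tables that cover a longer period than the plan's own safety outcome. The size in events is unknown and could be zero. It depends on the consent-to-surgery interval and the pre-operative AE rate, and the documents give neither. Efficacy, sample size, power and alpha are unaffected, and recording from consent is sound in itself.

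Three stronger readings are tempting, and the documents do not support them.
- *That device-related counts are contaminated.* Causality coding keeps most pre-surgery events out of those tables. What remains is a possible Softband event or one that cannot be assessed.
- *That comparison with the predecessor is distorted.* The indirect comparison in protocol 4.3 concerns performance variables, and neither 9.10.2 nor the SAP plans an AE comparison. Section 4.2.2.1.2 does not say whether the predecessor's events were counted from consent or from surgery.
- *That a percentage inflation can be projected from the predecessor's unrelated events.* That would apply a rate observed after implantation to the period before it, over an interval that is itself assumed.

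**What to change.** 1. Keep recording AEs from consent, as 7.4, 11.2 and the schedules have it. Reword the adverse event row in protocol Sections 2 and 6.2 so that surgery onwards is the analysis window and not the start of collection.
2. Add to SAP 3.4.4.14, and mirror in protocol 9.10.2, that Tables 14.3.1.x count AEs with onset on or after surgery, together with events that began earlier and worsened after surgery. State that such worsening is entered as a new record, because 11.2 otherwise keeps one record at its highest grade.
3. List pre-surgery AEs separately, including any related to the Softband reference device or to study procedures, so that nothing is lost from the report.

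The 3-month upper cut in SAP 3.5.1 can stay as it is. The cost is wording, one date filter on a field already collected, an instruction to sites on the new-record rule, and one short listing.

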11.2.1 Assessment of Severity

The Principal Investigator (or qualified delegate) will make an assessment of severity for each event based on clinical judgement. The intensity of each event recorded in the CRF should be assigned to one of the following categories:

Mild	An event that is easily tolerated by the subject, causing minimal discomfort and not interfering with everyday activities.
Moderate	An event that is sufficiently discomforting to interfere with normal activities
Severe	An event which is incapacitating and prevents normal everyday activities

11.2.2 Assessment of Causality

The Investigator will assess the potential causal relationship of each event, using clinical judgement. Alternative causes, such as natural history of underlying diseases, other risk factors and the temporal relationship of the event to the IMD product will be considered and investigated. The causal relationship to the IMD is to be assessed by the Investigator (or medically qualified delegate) and should be assessed using the following classifications:

Not related	
Relationship to the medical device or procedures can be excluded when:
 
 the event is not a known side effect of the product category the device belongs to or of similar devices and procedures; the event has no temporal relationship with the use of the device or the procedures; the event does not follow a known response pattern to the medical device (if the response pattern is previously known) and is biologically implausible; the discontinuation of medical device application or the reduction of the level of activation/exposure - when clinically feasible - and reintroduction of its use (or increase of the level of activation/exposure), do not impact on the event; the event involves a body-site or an organ not expected to be affected by the device or procedure; the event can be attributed to another cause (e.g. an underlying or concurrent illness/ clinical condition, an effect of another device, drug, treatment or other risk factors); the event does not depend on a false result given by the Investigational device used for diagnosis, when applicable; harms to the subject are not clearly due to use error; 
In order to establish the non-relatedness, not all the criteria listed above might be met at the same time, depending on the type of device/procedures and the event.

Unlikely related	The relationship with the use of the medical device seems not relevant and/or the event can be reasonably explained by another cause, but additional information may be obtained.

Possibly related	The relationship with the use of the medical device is weak but cannot be ruled out completely. Alternative causes are also possible (e.g., an underlying or concurrent illness/ clinical condition or/and an effect of another device, drug or treatment). Cases where relatedness cannot be assessed or no information has been obtained should also be classified as possibly related.
Probably related	The relationship with the use of the medical device seems relevant and/or the event cannot be reasonably explained by another cause, but additional information may be obtained.
Definitely related	
The event is associated with the medical device or with procedures beyond reasonable doubt when:
 
 • the event is a known side effect of the product category the device belongs to or of similar devices and procedures; • the event has a temporal relationship with the medical device use/application or procedures; • the event involves a body-site or organ that 
 – the medical device or procedures are applied to – the medical device or procedures have an effect on; • the event follows a known response pattern to the medical device (if the response pattern is previously known); • the discontinuation of medical device application (or reduction of the level of activation/exposure) and reintroduction of its use (or increase of the level of activation/exposure), impact on the event (when clinically feasible); • other possible causes (e.g., an underlying or concurrent illness/ clinical condition or/and an effect of another device, drug or treatment) have been adequately ruled out; • harm to the subject is due to error in use; • the event depends on a false result given by the medical device used for diagnosis, when applicable; 
In order to establish the relatedness, not all the criteria listed above might be met at the same time, depending on the type of device/procedures and the event.

